9.1.5 Definition of Unacceptable Toxicity

Toxicities will be graded according to the NCI CTCAE version 4 criteria. Any Grade 3 or any Grade 4 toxicity that is not reversible within 2 weeks, any life-threatening event deemed related to the study drug, or any treatment-related death will be considered unacceptable.

Any Grade 2 or higher autoimmune toxicities, particularly those affecting vital organs (e.g. cardiac, renal, CNS), will be considered an unacceptable toxicity, if it occurs within 2 weeks post-infusion. Grade 3 or higher surgical complications from insertion of the catheter are considered an unacceptable toxicity.

Exceptions to these unacceptable toxicities are as follows:

- Events associated with the biopsy procedure/catheter placement: Seizures or hemorrhages occurring during anesthesia or the biopsy/catheter insertion proper prior to administration of the agent if Grade 2 or lower.
- Seizures: Due to the nature of the disease under investigation in this protocol, patients may have pre-existing seizures or be susceptible to new seizures as a result of the underlying disease process. Although seizures may be defined as Grade 3 or 4 toxicities under NCI CTC, and will be reported as such in this protocol, seizures will not be considered an unacceptable toxicity if, in the opinion of the site Principal Investigator they have not increased in frequency or can be attributed to another recognized cause of increasing seizure frequency such as sub-therapeutic anti-convulsant levels or biopsy proven tumor progression.
- New or worsening neurologic deficits: Due to the nature of the disease under investigation in this protocol, patients may have an increase in pre-existing neurologic deficits or may develop new neurologic deficits as a result of tumor invasion. A new neurologic deficit, which resolves within 2 weeks after initiation of medical therapy, will not be considered an unacceptable toxicity. New neurological symptoms will not be an unacceptable toxicity if they can be ascribed to tumor progression (e.g. documented with histopathologic analyses of biopsy tissue), or they respond to treatment (e.g. oral steroids) within 2 weeks.
- Thromboembolism: While deep vein thrombosis (DVT) is not as common in children as in adults with malignant glioma, patients may have undiagnosed pre-existing DVTs or be susceptible to the development of DVTs due to the underlying disease process. Although DVT may be defined as Grade 3 or 4 toxicities under NCI CTC, and will be reported as such in this protocol, DVT will not be considered an unacceptable toxicity in this protocol.
- Syndrome of Inappropriate Antidiuretic Hormone (SIADH): Due to the high incidence of SIADH in this patient population, patients may be susceptible to the development of SIADH due to the underlying disease process. Although SIADH may be defined as Grade 3 toxicity under NCI CTC, and will be reported as such in this protocol, SIADH will not be considered an unacceptable toxicity in this protocol unless it is refractory to medical management.
- Muscle Weakness and Weight Gain: Due to the high incidence of muscle weakness and weight gain in patients taking steroids in this patient population, patients may be susceptible to the development of muscle weakness or weight gain which is due to steroids alone. Although muscle weakness may be defined as Grade 3 or 4 toxicity and weight gain $\geq 20\%$ may be defined as Grade 3 toxicity under NCI CTC, and will be reported as such in this protocol, muscle weakness or weight gain will not be considered an unacceptable toxicity in this protocol if the patient has required steroids greater than physiologic doses in the interval between the immunization and the development of the toxicity.

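### In Section 9.1.5 the seizure exception can override the rule that every drug-related life-threatening event counts, because its first test looks at seizure frequency and not at severity or cause

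*Combined protocol and SAP*

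**What the plan says.** Section 9.1.5 sets the base rule first. Grade 3 or 4 toxicity counts if it does not reverse within two weeks. Separately, and with no condition on reversibility, "any life-threatening event deemed related to the study drug, or any treatment-related death will be considered unacceptable".

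The list that follows opens with "Exceptions to these unacceptable toxicities are as follows", so each bullet qualifies everything above it. The seizure bullet acknowledges high grades: "Although seizures may be defined as Grade 3 or 4 toxicities under NCI CTC, and will be reported as such in this protocol". It then excepts them if, in the site investigator's judgement, "they have not increased in frequency or can be attributed to another recognized cause of increasing seizure frequency"; low anticonvulsant levels and progression shown on biopsy are given as examples of such a cause.

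Two other bullets in the list carry a severity limit. Seizures or hemorrhages around the procedure are excepted only when they occur during anesthesia or the "biopsy/catheter insertion proper prior to administration of the agent if Grade 2 or lower". SIADH is excepted only while it responds to treatment. The DVT bullet has no limit.

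The definition feeds the first primary endpoint (Table 1, Section 15.4.2) and the accrual suspension rule (Section 15.4.1, Table 4), both over 14 days after infusion.

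**The concern.** The bullet's stated purpose is to set aside seizures that belong to the underlying disease. Unchanged frequency is a poor marker of that when the character of the seizures has changed. A patient may have the same number of seizures as before while one of them is far worse, and the first limb of the exception does not ask about that. It also does not ask whether the event was judged related to the drug, which is the condition on which the base rule turns.

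The text therefore gives two answers for the same event, and the one placed later and framed as an exception removes it. Seizure is a plausible acute harm of an infusion into the brain, so the gap lies in an event class that the endpoint ought to capture. At stake are the primary safety percentage and the count that triggers a pause in accrual.

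**Working it through.** **1. The clauses side by side**

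| Question | Base rule | Seizure exception, first limb |
|---|---|---|
| Grade | Life-threatening counts | Grade 3 and 4 expressly covered |
| Relatedness | Must be deemed drug-related | Not mentioned |
| Severity change | Not needed | Not mentioned |
| Frequency | Not mentioned | Sole test, by investigator judgement |
| Baseline or counting window | Not needed | None defined in 9.1.5 |

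The two limbs are joined by *or*. The second, on another recognized cause, can only widen the exclusion. Nothing later in 9.1.5 restores a drug-related life-threatening seizure. A fatal seizure is less clear: the bullet names Grades 3 and 4 only, and treatment-related death is a separate item in the base rule.

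**2. A record that meets both clauses (hypothetical)**

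Before infusion: about 4 brief seizures per two weeks. In the 14 days after: 3 brief seizures and 1 prolonged life-threatening one deemed drug-related. Total 3 + 1 = 4, so frequency is unchanged. The base rule counts the patient; the exception, read literally, does not. In a patient with no previous seizures, a first seizure is itself an increase, so the first limb cannot apply. The gap is confined to patients with pre-existing seizures.

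**3. The plan's own figures**

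Inputs: Table 4 thresholds (2 or more at up to 6 patients, 3 or more at 7 to 9, 4 or more at 10 to 12) and a maximum of 12 patients (Section 15.9). An exact binomial recursion, checking after each patient and suspending when the threshold is reached, gives:

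| True probability | Table 5 | Recomputed |
|---|---|---|
| 0.05 | 0.030 | 0.035 |
| 0.10 | 0.124 | 0.128 |
| 0.15 | 0.262 | 0.260 |
| 0.20 | 0.411 | 0.408 |
| 0.25 | 0.560 | 0.555 |
| 0.30 | 0.681 | 0.686 |
| 0.35 | 0.792 | 0.793 |
| 0.40 | 0.873 | 0.872 |

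All are within 0.006. Table 5 is right for the events that the rule counts. The issue is which events those are.

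**4. Effect of one reclassified patient**

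- Primary percentage: 1/12 = 8.3 points. For example, 4/12 = 33.3% becomes 3/12 = 25.0%.
- Table 4: with 3 true cases among 9 patients, 2 counted is below the threshold of 3. With 4 true cases among 12, 3 counted is below the threshold of 4.

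**5. Sensitivity of the suspension rule (assumed rates)**

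Let s be the share of all patients whose only unacceptable event is an excepted seizure. The rule then sees p − s instead of p. The documents give no value for s.

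| True p | s = 0 | s = 0.02 | s = 0.05 | s = 0.10 |
|---|---|---|---|---|
| 0.30 | 0.686 | 0.636 | 0.555 | 0.408 |
| 0.40 | 0.872 | 0.844 | 0.793 | 0.686 |

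These are suspension probabilities from the start of a 12-patient study. They show the direction and steepness of the effect and do not estimate it.

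**The case against.** The strongest reply is that the test is a judgement. The investigator's opinion governs, and the bullet's stated rationale is disease-related seizures. An investigator who had just attributed a prolonged seizure to the drug could fairly say that prolonged seizures had risen from none to one. That stands: the text permits the exclusion but does not compel it. It does not remove the conflict, because the same text supports both answers.

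Second, the event would not be hidden. It is still graded and recorded. Section 15.4.2 tabulates events by maximum grade, both treatment-related and regardless of attribution. Section 13.2.1 sends serious events to the Sponsor within 24 hours, and the external board in Section 13.7 can recommend stopping enrollment. This stands too, and it limits the harm to the primary percentage and the automatic trigger, which itself only starts a review.

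Third, screening already includes a history and neurologic assessment (Sections 12.1 and 12.7.1), so a baseline could be reconstructed. That is partly right, but neither those sections nor Table 2 asks for seizure frequency or worst grade.

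Three stronger readings are tempting and are not supported:

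- *That milder seizures count while severe ones do not.* A single Grade 3 seizure that resolves within two weeks does not meet the base rule on its natural reading, so no such inversion follows.
- *That about four in ten such events would be lost.* With a stable Poisson baseline of L seizures per 14 days plus one drug-caused seizure, the chance that the total does not exceed L is P(Poisson(L) ≤ L − 1): 0.368, 0.406 and 0.433 at L = 1, 2 and 4. It is only 0.22 at L = 1.5 and zero below L = 1. The result depends on the L chosen, and the documents give none.
- *That a lost event could defeat the threshold of 2 in the first six patients.* Section 5.5 reports no dose-limiting toxicities in the first five. If that term means unacceptable toxicity, which the protocol does not say, this threshold can no longer be reached. The later thresholds of 3 and 4 remain.

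**Conclusion.** Section 9.1.5 contradicts itself for one narrow class: a seizure in a patient with pre-existing seizures that is drug-related and life-threatening, or irreversible at Grade 3 or 4, and is more severe without being more frequent. Followed as written, the exception can drop that patient from the 14-day primary percentage and the Table 4 count.

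One such patient among 12 shifts the percentage by 8.3 points and can decide whether a remaining threshold is reached. How often this would occur cannot be stated from the documents. The conclusion rests on reading the exceptions as overriding the whole base rule, as their opening line indicates, and on the investigator applying the frequency test literally. No stated figure in the plan is wrong, and disclosure of the event is not at issue.

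**What to change.** Reconcile the two clauses of Section 9.1.5 with two edits and one data item:

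1. State that the seizure exception does not remove a life-threatening or fatal seizure deemed related to study drug.
2. Change the first limb to: *not increased in frequency or severity (CTCAE grade) compared with the pre-infusion baseline*.
3. Record pre-infusion seizure frequency and worst grade on the eCRF, from the screening history already taken.

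This brings the bullet into line with the procedural and SIADH exceptions, which already carry a severity limit. It changes an endpoint definition and no aspect of treatment. The cost is a phrase, a sentence and a short eCRF entry. The downside is that a few severe seizures caused by the tumor may be counted, although the attribution limb still removes non-life-threatening ones with another recognized cause.

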7.3 Study Purpose/Rationale

Outcome for children with recurrent malignant glioma, especially GBM, is dismal with currently available therapeutic modalities. The blood-tumor barrier is a major impediment to therapy and approaches that bypass this barrier may be required. Oncolytic immunotherapy is a promising biologic approach to treatment that not only induces viral mediated tumor destruction, but also harnesses a complex immune response that can serve in disease control. The genetically engineered oncolytic PV (PVSRIPO) has tropism for tumor cells by virtue of expression of CD155 in tumor cells. To facilitate concentration of the therapeutic agent at the tumor site, while minimizing systemic exposure, PVSRIPO will be delivered directly into the tumor. Significant pre-clinical anti-tumor activity of PVSRIPO has been observed in several rodent tumor models and *in vitro*. PVSRIPO was devoid of neuropathogenicity when injected into the thalamus of non-human primates even at doses as high as 5×10^9 TCID. Also, the phase I trial of PVSRIPO in adults with recurrent WHO grade IV malignant glioma still in the follow-up phase did not yield evidence of viral encephalomyelitis, poliomyelitis or meningitis with a proportion of patients enjoying prolonged disease survival up to 58+ months. The main toxicity attributable to PVSRIPO has been post-treatment peri-tumoral inflammation that has required prolonged steroid therapy and/or low dose bevacizumab to control edema. CD155 expression in pediatric GBM has been confirmed in 10 tumor samples. Therefore, a phase Ib study should be conducted in this high-risk pediatric population to evaluate feasibility, safety, and preliminary evidence of efficacy of the selected adult dose (5×10^7 TCID).

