12.7.3 Radiographic Review

A CT will be obtained to confirm catheter placement prior to beginning the PVSRIPO infusion. A MRI of the brain without gadolinium enhancement will be obtained within 4 hours of

completing the PVSRIPO infusion to monitor distribution of the infusion. A MRI of the brain with gadolinium enhancement will be obtained at all subsequent visits.

Given that imaging following immunotherapy differs greatly from what is typically seen following chemoradiation treatment or treatment with anti-angiogenic compounds, evaluation of response using with Macdonald criteria or RANO criteria is not appropriate in this trial. Immunotherapy can trigger an inflammatory immune response that is observed on imaging. Distinguishing between the inflammatory immune response and progressive disease is difficult. Therefore, an exploratory objective of this study is to describe radiographic imaging post-PVSRIPO treatment. Another exploratory objective of this study is to describe changes in tumor volume based upon radiographic imaging. For that reason, subjects who have gone off study may continue to be followed for collection of MRI measurements. For the purpose of this objective, relative tumor volume is estimated from the MRI using the metric of multiplying the widest tumor diameter with the perpendicular height of the tumor in that same slice.

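### Section 9.1.5: the neurologic exception has two recovery tests and no grade limit, so a severe new deficit that improves but persists can drop out of the 14-day endpoint and the Table 4 count

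*Combined protocol and SAP*

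**What the plan says.** The main rule in section 9.1.5 counts "Any Grade 3 or any Grade 4 toxicity that is not reversible within 2 weeks", and adds that "any life-threatening event deemed related to the study drug, or any treatment-related death will be considered unacceptable". A further criterion counts autoimmune toxicity of Grade 2 or higher within 2 weeks of infusion and names the CNS among the organs of concern. The list that follows is introduced as a set of exceptions to all of these. Its bullet on neurologic deficits offers three ways out:

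- "A new neurologic deficit, which resolves within 2 weeks after initiation of medical therapy, will not be considered an unacceptable toxicity";
- new symptoms do not count when they are put down to tumor progression, for which tissue histology is given only as an example of evidence;
- new symptoms are also exempt under a second recovery test, worded "or they respond to treatment (e.g. oral steroids) within 2 weeks".

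The bullet has no grade limit. The bullet on biopsy and catheter events in the same list does: Grade 2 or lower.

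The definition is used twice. It gives the first primary endpoint, the 14-day percentage (Table 1, section 15.4.2). It also gives the Table 4 count (section 15.4.1), which suspends accrual at 2 or more patients with up to 6 accrued, 3 or more at 7 to 9, and 4 or more at 10 to 12.

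Other measures stand beside it. Section 15.4.2 reports, also under the primary objective, the proportion of patients needing low-dose bevacizumab or steroids for an inflammatory reaction to PVSRIPO. It also tabulates all adverse events by maximum grade regardless of attribution. The long-term rule in section 15.4.1 interrupts enrollment if one inflammatory reaction shows no improvement within 18 weeks of starting treatment.

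**The concern.** The bullet is justified by tumor invasion, but its two recovery routes do not require the tumor to be the cause. Section 7.3 states that "The main toxicity attributable to PVSRIPO has been post-treatment peri-tumoral inflammation". Section 9.1.6 lists focal deficits and coma among the presentations of cerebral edema, and paresis and paralysis among the possible complications of the virus. The exception therefore falls on a kind of event that the drug itself might produce.

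The route through progression rests on judgment. Histology is only an example, section 12.7.3 says "Distinguishing between the inflammatory immune response and progressive disease is difficult", and for patients enrolled after October 31, 2019 the first post-infusion MRI in Table 2 is at Week 4.

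With at most 12 patients, and a threshold of 2 among the first 6, the classification of one child can decide whether accrual is suspended.

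**Working it through.** **1. The wording applied to four cases**

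| New neurologic event within 14 days | Main criteria | Neurologic bullet | Result |
|---|---|---|---|
| Grade 3 or 4 deficit, improved but still present after 2 weeks of therapy | counted | fails *resolves*, passes *respond* | can be left out |
| Drug-related life-threatening event that responds | counted | passes *respond*; no grade limit | left out on literal wording |
| CNS autoimmune toxicity, Grade 2 or higher, that responds | counted | passes *respond* | unreconciled |
| Symptoms ascribed to progression without tissue | may be counted | exempt | left out |

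The reversibility clause may qualify Grade 4 alone or Grades 3 and 4 together. Row 1 holds on both readings, because the deficit has not reversed. If the clause covers Grade 4 only, the bullet also removes Grade 3 deficits that resolve, which the main rule would count.

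**2. Does another stated rule halt accrual for row 1?** The second primary endpoint and the adverse-event tables carry no threshold. The long-term rule has one, but it too tests improvement, so a deficit that partly improves does not meet it. Row 4 can also miss the second primary endpoint, which depends on attribution to PVSRIPO.

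**3. Reproducing Table 5.** Let p be the true 14-day rate, q = 1 − p, and b(j) = C(3,j) p^j q^(3−j). Counts never fall and the threshold is constant within each band, so the suspension probability can be obtained at patients 6, 9 and 12:

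- after 6: A0 = q^6, A1 = 6pq^5;
- after 9: B0 = A0·b(0); B1 = A0·b(1) + A1·b(0); B2 = A0·b(2) + A1·b(1);
- never suspended = B0 + B1·[1 − b(3)] + B2·[b(0) + b(1)].

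At p = 0.30: A0 = 0.1176 and A1 = 0.3025; B0 = 0.0404, B1 = 0.1557 and B2 = 0.1557. Never suspended = 0.0404 + 0.1557 × 0.973 + 0.1557 × 0.784 = 0.314. The suspension probability is 0.686; Table 5 gives 0.681. All eight rows agree within 0.005.

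**4. Illustration.** Suppose a share f of patients with an unacceptable toxicity is exempted and has no other counted event. The counted rate is then p(1 − f). Both p and f are assumptions; the documents give neither.

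| p | f | Counted rate | Suspension probability, Table 5 (recomputed) |
|---|---|---|---|
| 0.30 | 0 | 0.30 | 0.681 (0.686) |
| 0.30 | 1/3 | 0.20 | 0.411 (0.408) |
| 0.30 | 2/3 | 0.10 | 0.124 (0.128) |
| 0.20 | 0 | 0.20 | 0.411 (0.408) |
| 0.20 | 1/2 | 0.10 | 0.124 (0.128) |
| 0.40 | 0 | 0.40 | 0.873 (0.872) |
| 0.40 | 1/2 | 0.20 | 0.411 (0.408) |

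**The case against.** A reader might infer that the main expected toxicity of the drug goes largely uncounted. The documents do not support that. Inflammation needing steroids or bevacizumab is itself an endpoint under the primary objective, with Kaplan-Meier time to treatment. A deficit exempted because steroids worked would appear there if attributed to PVSRIPO. All adverse events are tabulated by grade, serious events go to the Sponsor within 24 hours whether or not related (section 13.2.1), and an external DSMB-Plus can recommend stopping enrollment (section 13.7). This objection stands, and it limits the point to the 14-day percentage and the Table 4 count.

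A reader might also infer that the seizure exception requires tissue proof and that the neurologic one should match it. It does not. Its phrase "sub-therapeutic anti-convulsant levels or biopsy proven tumor progression" only gives examples of recognized causes, and the judgment is left to the investigator. Section 9.1.4 places later biopsies outside the protocol, so a histology mandate would count true progression as toxicity whenever no tissue was taken.

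The bullet never mentions life-threatening events, death or edema, so the override is a literal reading of the list's opening and not a stated intention. A treatment-related death can neither resolve nor respond, so these two routes cannot exempt it. Despite the bullet's title, its operative sentences cover new deficits and symptoms, not worsening of old ones.

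Finally, the study is descriptive, Table 4 leads to review and not automatic termination, and section 5.5 reports no dose-limiting toxicities in the first 5 patients. The documents give no separate definition of that term, though. If section 9.1.5 was used, the same exception applied to that review.

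**Conclusion.** The defect is in the text itself: two recovery tests in adjacent sentences, the looser one undefined and sufficient alone, no grade limit, and an unreconciled overlap with the drug-related life-threatening and CNS autoimmune criteria. A severe new deficit that improves but persists can leave the first primary endpoint and the only acute suspension count. Because these govern a pediatric safety study, the wording should be corrected.

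The size cannot be estimated. The fall in suspension probability from about 0.68 to 0.41 assumes a true rate of 0.30 and one third of events exempted. It shows that the rule is sensitive to the wording, not that such a loss has occurred. Some exempted events will be genuine progression, so not every exempted event is lost signal.

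**What to change.** In section 9.1.5:

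1. Reconcile the two sentences to a single defined recovery standard, consistent with the main rule's reversibility test, and make clear whether that test qualifies Grade 3 as well as Grade 4.
2. State that the exception does not remove an event meeting the drug-related life-threatening criterion, and reconcile the bullet with the CNS autoimmune criterion.

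In sections 15.4.1 and 15.4.2:

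3. Report the 14-day percentage and the Table 4 count with and without events exempted under this bullet, showing separately those ascribed to progression without tissue.
4. Re-tabulate the patients already treated in the same two ways. Showing both counts avoids relying on a reclassification made with outcomes known in an open-label study.

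Histology should not be made mandatory.

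The cost is amendment wording and a second look at events in a few patients, with no new procedure. The downside is that the reported toxicity percentage may rise and more events may count toward suspension, by an amount that the documents do not allow one to state.

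### Section 9.1.5 exempts every DVT from unacceptable toxicity, although its stated reason covers only pre-existing or disease-related DVT

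*Combined protocol and SAP*

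**What the plan says.** Section 9.1.5 first gives the general rules. One is "Any Grade 3 or any Grade 4 toxicity that is not reversible within 2 weeks". Another is that "any life-threatening event deemed related to the study drug, or any treatment-related death will be considered unacceptable". Separate sentences cover early autoimmune toxicity and Grade 3 or higher surgical complications of catheter insertion.

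A list follows, introduced by "Exceptions to these unacceptable toxicities are as follows". The bullet labelled Thromboembolism:

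- opens with a concession: "While deep vein thrombosis (DVT) is not as common in children as in adults with malignant glioma";
- gives its reason: "patients may have undiagnosed pre-existing DVTs or be susceptible to the development of DVTs due to the underlying disease process";
- acknowledges severity: "Although DVT may be defined as Grade 3 or 4 toxicities under NCI CTC, and will be reported as such in this protocol";
- concludes: "DVT will not be considered an unacceptable toxicity in this protocol".

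The definition is used twice. Section 15.4.2 (and Table 1) makes the percentage of patients with unacceptable toxicity in the 14 days after infusion a primary endpoint. Section 15.4.1 uses the same definition for the Table 4 accrual-suspension thresholds: 2 or more patients among the first 6, 3 or more at 7 to 9, and 4 or more at 10 to 12. Section 15.9 caps the trial at 12 treated patients.

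**The concern.** The exception has no condition on grade, cause, relatedness or reversibility. Its reason concerns clots that the patient already had or that the tumour brought on. Its wording goes further and also removes a clot that the investigator attributes to the study drug. If that clot is life-threatening, it is an event that the general rule was written to count.

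The edge of the exception is also unclear. The label is broader than the text, which names only DVT and only Grades 3 and 4. It does not say whether a clot that embolises is covered, whether a fatal related clot stays under the treatment-related-death rule, or what happens when a DVT is judged a Grade 3 or higher complication of catheter insertion. Two assessors could classify the same event differently. In a trial of at most 12 children, one classification visibly changes the primary result and the monitoring count.

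**Working it through.** **Step 1. Compare the exceptions in Section 9.1.5.**

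| Exception | Limit attached |
|---|---|
| Biopsy or catheter events (seizure, hemorrhage before infusion) | Only up to Grade 2 |
| Seizures | No rise in frequency, or another recognised cause |
| Neurologic deficits | Resolution or response within 2 weeks, or ascribed to progression |
| SIADH | "unless it is refractory to medical management" |
| Muscle weakness, weight gain | Steroid use above physiologic dose beforehand |
| Thromboembolism (DVT) | None |

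**Step 2. Ask which general rule the stated reason needs to displace.** The non-reversible Grade 3 or 4 rule has no relatedness condition, so without an exception a tumour-related DVT could count under it. The exception is useful there. The rules for life-threatening events and for death already require relatedness to the drug or treatment. A DVT that is pre-existing or due to the tumour, and is attributed that way, does not meet them. Restoring those two rules for DVT therefore takes nothing away from the exception's stated purpose.

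**Step 3. Trace one event.** Take a DVT within 14 days of infusion that is life-threatening and deemed related to PVSRIPO.

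- General rule alone: unacceptable, so it counts in the primary percentage and in Table 4.
- With the exception as written: it counts in neither.

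**Step 4. Reproduce Table 5, which depends on the definition.** I applied the Table 4 rule after every patient by exact binomial recursion, with a maximum of 12.

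| True probability | Suspension: stated / exact | Expected N: stated / exact |
|---|---|---|
| 0.05 | 0.030 / 0.035 | 11.8 / 11.75 |
| 0.10 | 0.124 / 0.128 | 11.1 / 11.11 |
| 0.15 | 0.262 / 0.260 | 10.2 / 10.21 |
| 0.20 | 0.411 / 0.408 | 9.2 / 9.19 |
| 0.25 | 0.560 / 0.555 | 8.1 / 8.15 |
| 0.30 | 0.681 / 0.686 | 7.2 / 7.15 |
| 0.35 | 0.792 / 0.793 | 6.2 / 6.24 |
| 0.40 | 0.873 / 0.872 | 5.4 / 5.45 |

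The largest gap in suspension probability is 0.005, so the table reproduces. It is indexed by the probability of a counted event. Changing which events count changes which row applies, not the rows themselves.

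**Step 5. Size per event.** Primary percentage: 1/12 = 8.3 points at full accrual. Table 4: one count, which is one of three at patients 7 to 9 and one of four at patients 10 to 12.

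**Step 6. Frequency.** The documents give no rate. Section 5.5 says 5 patients had been treated when the 14-day stagger was lifted, leaving 12 - 5 = 7 places. Assume, for illustration only, a rate of 1% to 3% per patient for a DVT that is life-threatening, related and within 14 days. The chance of at least one among 7 is then 1 - 0.99^7 = 6.8% to 1 - 0.97^7 = 19.2%. Nothing in the documents supports those rates, and the verdict does not use them.

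**The case against.** A reader might infer that Section 9.1.5 contradicts itself. It does not. The list is expressly one of exceptions, and the DVT bullet names Grades 3 and 4 before exempting them, so for DVT the specific text overrides the general rule. The documents give one answer; the question is whether that answer is wider than intended.

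A reader might also take the reason to be background frequency, undercut by the remark that DVT is less common in children. That remark is a concession made before the actual reason. High incidence is the reason given for SIADH and for muscle weakness and weight gain, not for DVT.

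Nor do the documents say that embolism is exempt. Only the one-word label is broader than DVT, and because the text names Grades 3 and 4 only, a treatment-related death is not clearly displaced. This is an ambiguity, not an exemption.

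It is tempting to say that one such event is half the suspension threshold among the first 6 patients. Section 5.5 reports no dose-limiting toxicities in the first 5. If that means no unacceptable toxicity, at most one can arise by patient 6, the threshold of 2 cannot be met, and the point is moot.

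Finally, the event would not be hidden. It is reported at its grade and tabulated both by relatedness and regardless of attribution (Section 15.4.2). A serious event goes to the sponsor within 24 hours, and an unexpected life-threatening suspected reaction goes to the FDA within 7 days (Section 13.2.1). The investigator and statistician review toxicity trends (Section 13.1.2), and the DSMB-Plus may recommend stopping enrollment (Section 13.7). All of that stands. But none of these channels puts the event into the primary percentage or the Table 4 count, so the gap in those two places remains.

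**Conclusion.** The point holds as an over-broad, unconditional exception with an unclear boundary. A life-threatening DVT deemed related to the study drug would be missing from the 14-day primary percentage and from the automatic suspension trigger, although the exception's stated reason does not reach it. Each such patient is worth 8.3 points at 12 treated patients and one Table 4 count. No figure in the plan is wrong, and Table 5 stands.

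How often this would matter cannot be estimated from the documents. Section 9.1.6 names no thrombosis risk for PVSRIPO itself. It does name thromboembolic events for bevacizumab, but the use set out there begins after the first 2 weeks, outside the endpoint window. The event is therefore likely to be rare. The case for acting is that the correction is cheap and the trial is small enough for one event to show.

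**What to change.** Amend the thromboembolism bullet in Section 9.1.5 as follows:

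1. Limit the exception to DVT that is pre-existing or attributed to the underlying disease, and state that the existing rules for related life-threatening events and treatment-related death still apply to DVT.
2. State how the exception relates to the existing rule on Grade 3 or higher complications of catheter insertion. No new criterion for the delivery procedure is needed.
3. Make the label match the text by stating that only DVT is exempt, so that embolism falls under the general rules.

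Then reclassify the patients already treated from the recorded grade and attribution (Sections 13.1 and 13.1.2). Given Section 5.5, this will probably change nothing for the first 5, but it should be documented.

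The cost is a short amendment, initiated by the sponsor and approved by the IRB (Section 16.6), that alters an endpoint definition after at least 5 of 12 patients were treated. A rare event may now be counted that the present text leaves out. No new data are needed, and tumour-related DVT stays exempt as intended.
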